## 8.2 Clinical laboratory evaluation

Analysis of clinical laboratories data will be performed by treatment for Hematology and Biochemistry tests. In case of different units of measure considered for the same laboratory

# PPD

parameter, all values will be converted into Standard International (SI) units (if applicable) or to the same unit.

The following summaries will be provided:

- A summary table showing for all laboratory tests the values and changes from baseline to each subsequent visit;
- A summary table showing for all laboratory tests the frequency of patients reporting an abnormal (clinically or not clinically significant) laboratory value at baseline and at subsequent visits.
- Shift tables presenting the number and the percentage of patients in each bivariate category (baseline versus each post-baseline visit) with regards to investigator's interpretation.

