### Discontinuation criteria

Administration of the investigational medicinal product will be discontinued in case the QTcF becomes either >500 msec. or increases by >60 msec. from baseline measurement on two consecutive measurements 1 hour apart, or if the patient develops any significant cardiovascular disease/abnormality. Similarly, administration of the investigational medicinal product will be discontinued in the case the patient develops renal (eGFR <60mL/min/1.73 m^2) or hepatic (ALT/AST >3 x ULN and total bilirubin >3mg/dL) dysfunction as well as hypoalbuminemia (serum albumin <3 g/dL). Lastly, administration of the investigational product will be immediately discontinued if the patient becomes pregnant, develops any significant systemic infection that must be assessed on a case-by-case basis by the investigator regarding whether they are serious enough to warrant discontinuation, ketoacidosis or hypoglycemic coma. Occurrence of any condition that qualify the patient to treatment discontinuation will be specifically monitored through ECG readings and laboratory tests obtained at visits scheduled at the end of the 3rd (Week 11), 6th (Week 23), 9th (Week 35) treatment cycles. In addition, the investigational medicinal product will be immediately discontinued in the event of any other possibly drug related occurrences that the Investigator believes might compromise patient's safety.

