#### 6.4.2. Criteria for discontinuation of the IMP

The IMP will be discontinued in the case:

- QTcF is either  $> 500$  msec or increases by  $> 60$  msec from screening measurement on two consecutive ECG readings taken 1 hour apart;
- The patient develops any significant cardiovascular disease/abnormality;
- The patient develops renal (calculated eGFR  $< 60$  mL/min) or hepatic (increased ALT/AST  $> 3 \times$  ULN and increased total bilirubin  $> 3$  mg/dL [ $> 51.3 \mu\text{mol/L}$ ]) dysfunction as well as hypoalbuminemia (serum albumin  $< 3$  g/dL);
- Pregnancy occurs (female patient);
- The patient develops any significant systemic infection that must be assessed on a case-by-case basis by the investigator regarding whether they are serious enough to warrant discontinuation.
- The patient develops ketoacidosis or hypoglycemic coma.

Occurrence of any condition that qualify the patient to treatment discontinuation will be specifically monitored through ECG readings and laboratory tests obtained at the visits scheduled at the end of the 3rd (Week 11), 6th (Week 23) and 9th (Week 35) treatment cycles.

In addition, the IMP will be immediately discontinued in the event of any other possibly drug related occurrences that the Investigator believes might compromise patient's safety.

If the IMP administration is prematurely discontinued, the primary reason for discontinuation must be recorded in the eCRF. Patients who discontinue the treatment with the IMP will NOT be withdrawn from the study by default, but will be asked to complete safety and efficacy observations as per the protocol, unless otherwise they withdraw their consent.

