## 7.3. TREATMENT PERIOD AND CHECK OF TREATMENT DISCONTINUATION CRITERIA

After the treatment has started, IMP administration will proceed for **additional 12 cycles** of 14 days on/14 days off, unless there is any reason for drug discontinuation (see **Section 6.4.2**). On each treatment

cycle, the IMP will be administered at 12 hours interval (morning and evening; ideally in between 6.30/11.30 and 18.30/23.30). At each administration, 2 capsules will be swallowed with a glass of water, at least 2 hours apart from breakfast or dinner.

During treatment, occurrence of any condition that might prevent continuing IMP administration will be verified at the visits scheduled during treatment (see below in section 7.4.1) at the end of the 3rd (Week 11), 6th (Week 23) and 9th (Week 35) treatment cycles.

During these visits the following will be measured/assessed (as per center practice actual date and time of assessment, or the date of sampling, will be recorded in the eCRF):

- Vital signs.
- Blood sampling(s) for measurement (local laboratories) of “Safety Laboratory Tests”.
- Evaluation of renal and hepatic function (to be derived from the safety laboratory test results).
- 12 lead ECG, performed using local equipment that allows automatic calculation of the QTcF.
- Pregnancy test (urine dipstick or blood sample).
- Patient Diary check (IMP administration information).

As per discontinuation criteria (see [Section 6.4.2](#)), **no IMP will be dispensed** in the case:

- QTcF is either > 500 msec or increases by > 60 msec from screening measurement on two consecutive ECG readings taken 1 hour apart;
- The patient develops any significant cardiovascular disease/abnormality;
- The patient develops renal (calculated eGFR < 60 mL/min) or hepatic (increased ALT/AST > 3 x ULN and increased total bilirubin > 3mg/dL [ $>51.3 \mu\text{mol/L}$ ]) dysfunction as well as hypoalbuminemia (serum albumin <3 g/dL);
- Pregnancy occurs (female patient);
- The patient develops any significant systemic infection that must be assessed on a case-by-case basis by the investigator regarding whether they are serious enough to warrant discontinuation.
- The patient develops ketoacidosis or hypoglycemic coma.

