## 11.4. DOCUMENTATION REQUIRED PRIOR TO INITIATION OF AND DURING THE STUDY

In addition to the documents mentioned in [Sections 10.1](#) and [12.1](#), the following documents will be required from the Investigator prior to the initiation visit (and during the course of the study in case of any update):

- Current, signed and dated Curriculum Vitae of Principal Investigator and any Sub-Investigators/co-workers. Updates should be provided at least every two years.
- Confidential disclosure agreement Form in accordance also with European data protection Regulation (EU) No. 679/2016 (GDPR)
- Normal ranges of all laboratory tests to be performed at the study site and a recent certification or accreditation of established quality control (or other documentation of established quality control or external quality assessment or other validation). Updates should be provided as soon as any reference value has changed.
- A signed page of the final protocol and any amendments.
- A signed copy of the study Financial Agreement/Clinical Study Agreement with Dompé (or CRO appointed by Dompé), including all study specific costs.
- List and any updates of delegated responsibility (Study Team Signature List / Delegation of Responsibilities form).
- Form 1572 and financial disclosure form 3455 from all the persons listed on the 1572. If applicable, the PI will provide an updated financial disclosure agreement to the Sponsor 1 year after the completion of the study.

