## 5.3 Permanent treatment discontinuation criteria

A summary table showing at each available time point the number and percentages of subjects who discontinued the study treatment along with the discontinuation criteria will be produced by treatment group. The number of patients still under treatment of discontinuing at the specific visit will be used as denominator for percentages.

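### SAP 8.2 gives no by-arm count of patients whose ALT or AST ever passed 3 x local ULN without meeting the joint stopping rule: a low-severity, low-cost addition

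*SAP*

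**What the plan says.** SAP 8.2 lists three laboratory outputs. The first is "A summary table showing for all laboratory tests the values and changes from baseline to each subsequent visit". The second gives "the frequency of patients reporting an abnormal (clinically or not clinically significant) laboratory value at baseline and at subsequent visits". The third is a set of shift tables, baseline against each later visit, in the investigator's categories. Where sites report in different units, "all values will be converted into Standard International (SI) units (if applicable) or to the same unit". The section does not mention reference ranges, a worst post-baseline value or unscheduled samples.

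The tests are run at the sites. The Protocol 7.3 visit list has the entry "Blood sampling(s) for measurement (local laboratories) of" the safety tests, and Protocol 11.4 requires from each investigator "Normal ranges of all laboratory tests to be performed at the study site", updated when a reference value changes.

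The synopsis defines the liver stopping limit as "hepatic (ALT/AST >3 x ULN and total bilirubin >3mg/dL) dysfunction". Both parts are required. The transaminase part is a multiple of ULN and the bilirubin part is an absolute value. Protocol 6.4.2 repeats the limit in a list that opens "The IMP will be discontinued in the case".

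SAP 5.3 adds a table by time point in which "the number and percentages of subjects who discontinued the study treatment along with the discontinuation criteria will be produced by treatment group". SAP 4.7 keeps patients with missing data in percentage denominators, shows them in a separate row, and allows exceptions if they are noted.

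**The concern.** The protocol sets its transaminase limit as a multiple of the local ULN, and the laboratory tables carry no ULN. They are also organised by visit, and a count at each visit is not a count of patients. Take a patient whose ALT passes 3 x ULN with bilirubin below 3 mg/dL, who feels well, and whose investigator calls the result abnormal but not clinically significant. That patient meets no laboratory stopping limit and may never become an adverse event. In SAP 8.2 the patient is one more abnormal value at one visit, with no indication of its size relative to the normal range.

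The protocol's own data give some reason to look at the liver. In the three-month rat study some liver enzymes rose in males at 150 mg/kg, and hepatocellular hypertrophy was seen in males at all doses; the findings recovered or tended to recovery (Protocol 2.2). In the earlier trial in type 1 diabetes one ladarixin patient stopped treatment for raised ALT and AST (Protocol 2.4.3). That trial gave three cycles and this one plans up to thirteen. Enrolment was stopped early and SAP 4.8 makes all analyses descriptive, so safety is a large part of what the trial can still report.

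**Working it through.** The plan states no figure on this point, so there is none to reproduce. The check asks what the planned outputs can and cannot show.

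**1. Where each kind of rise is counted by arm**

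| Rise | Where it is counted |
|---|---|
| ALT/AST >3 x ULN with bilirubin >3 mg/dL | SAP 5.3, because stopping is required (Protocol 6.4.2) |
| Transaminases alone, an adverse event that leads to stopping | SAP 8.1 (overview count of patients stopping for a TEAE; table of such TEAEs) and SAP 5.5 (reasons) |
| Transaminases alone, an adverse event, treatment continued | SAP 8.1, by preferred term, without size |
| Transaminases alone, not an adverse event, treatment continued | SAP 8.2 by visit only, plus listings |

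In the third row, patients are counted once per preferred term. ALT increased and AST increased are separate terms (the earlier trial's patient had both), so the two lines cannot be added to give patients. The fourth row is the gap: Protocol 8.2 makes a laboratory change an adverse event only if it is clinically relevant.

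**2. From visit counts to patients.** The number of patients ever abnormal lies between the largest visit count and the sum of the visit counts. SAP 3.7 has five scheduled post-baseline visits. With counts of 1, 1, 1, 1, 1 the bounds are 1 and 5.
- Planned ladarixin arm, 75 x 2/3 = 50: 1/50 = 2% to 5/50 = 10%.
- Assumed arm of 20 (the final size is not in the documents): 1/20 = 5% to 5/20 = 25%. The Clopper-Pearson 95% limits are 0.1% to 24.9% for 1 patient and 8.7% to 49.1% for 5.

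**3. From a raw value to a multiple of ULN.** A value of 120 U/L exceeds 3 x ULN only if the ULN is below 120/3 = 40 U/L. For an assumed local ULN of 33 U/L the multiple is 120/33 = 3.6; for 55 U/L it is 120/55 = 2.2. The printed value alone does not settle it.

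**4. What one such patient does to the value table.** With the other patients at an assumed 20 to 30 U/L, the arm mean moves by (120 - 20)/50 = 2.0 to (120 - 30)/50 = 1.8 U/L for 50 patients, and by 5.0 to 4.5 U/L for 20. The median barely moves. SAP 4.1 also prints the maximum, so an outlier of 120 U/L would be visible at that visit.

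**5. Denominator.** If 25% of tested patients are abnormal, keeping untested patients in the denominator prints 0.25 x 0.90 = 22.5% with 10% untested and 0.25 x 0.80 = 20% with 20% untested.

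**6. What is known, and what a table could find.** The earlier trial had 1/50 on ladarixin (95% CI 0.05% to 10.6%) and no such stop reported among 26 on placebo (upper limit 13.2%); Fisher p = 1.00. If the true rate were 2%, the chance of at least one case would be 1 - 0.98^50 = 64% with 50 patients and 1 - 0.98^20 = 33% with 20.

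**The case against.** The case against is substantial. SAP 8.2 delivers what Protocol 9.5.4 promises: descriptive statistics by visit, frequencies of abnormal and clinically significant values, and shift tables. No safety endpoint names a threshold count. SAP 4.1 prints each arm's maximum at each visit. SAP 10.1 sorts the listings by treatment group, patient and visit, so in a small trial a reader could count patients with high raw values by hand. Investigators presumably judge abnormality against their own site's range, so the abnormal categories already come close to a 1 x ULN band. Protocol 6.4.2 also requires stopping for any possibly drug-related occurrence that the investigator thinks might compromise safety. The mock shells are a separate file that was not available, and they may contain more.

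All of this stands, and it rules out two stronger readings. A reader might infer that the SAP breaches the protocol; it does not. A reader might also infer that a case like the earlier trial's would be lost; it would be counted in the overview of patients stopping for a TEAE and in the discontinuation reasons.

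What survives is narrower. No listed output gives the multiple of the local ULN, and none counts by arm the distinct patients with an isolated rise who stayed on treatment and had no adverse event reported. Listings do not close the gap unless the local ULN is held with each value, and the SAP does not say that it is.

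**Conclusion.** The point holds as a low-severity improvement to the SAP text. The loss is in the sensitivity and readability of the liver data: in the illustration, the by-visit tables cannot tell 1 patient from 5. The percentages rest on the planned arm of 50 or an assumed arm of 20, and the multiples rest on assumed ULNs of 33 to 55 U/L.

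A reader might infer a biased comparison between arms. The documents do not support that for the blinded period: randomisation is stratified by site, so local ranges should be spread over both arms, and the same tables apply to each. Protocol 3.3 breaks the blind after the last patient's Month 12 visit, so some Month 18 investigator classifications may be made open-label. A reader might also infer an established liver signal; one case in 50 against none reported in 26 cannot show one. The added table may itself be empty, which would still be worth reporting.

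The denominator rule is a lesser matter, because the row for missing patients lets a reader recompute the percentages.

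**What to change.** In SAP 8.2, divide ALT, AST and total bilirubin by the reporting laboratory's ULN in force on the sample date. Add one table by arm of patients whose worst post-baseline value, over scheduled, unscheduled and withdrawal samples, has:
- ALT or AST >3 x ULN;
- ALT or AST >3 x ULN with bilirubin >3 mg/dL, mainly as a check on SAP 5.3, stating whether both must be met on the same sample.

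The denominator is patients with at least one post-baseline result. Both limits are the protocol's own; other bands are optional and may be mostly zeros in a small trial. For by-visit laboratory abnormality percentages, use patients with a result at that visit, as a noted exception to SAP 4.7.

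The cost is a few lines of SAP text, one table, and the data work. Protocol 11.4 collects normal ranges as site documents, so they may have to be entered in the analysis database and matched by laboratory and date. No new patient data are needed.

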## 8.3 Vital signs

Summary statistics by treatment will be provided along with summary of the change from baseline at each time point for the following vital signs:

- Systolic Blood Pressure (mmHg),
- Diastolic Blood Pressure (mmHg), and
- Heart Rate (bpm);

## 8.4 ECGs

Summary statistics by treatment of QTcF Interval (msec) and ECG interpretation (Normal, Abnormal NCS, Abnormal CS, No Result) will be provided along with summary of the change/shift from baseline at each time point.

In case of repetition of ECG evaluation (according to protocol), the repeated QTcF value will be considered as the only evaluation value for that visit.

## 8.5 Pregnancy test over the study

A summary table showing test results (Negative/Positive) over the study will be produced by treatment group, where applicable.

## 9. Derivations and date conventions

### 9.1 Variable derivation

# PPD

Table 3: Variable derivation rules

Parameter	Calculation
HbA1c <7% and daily insulin requirement <0.50 IU/Kg/day at Time point Tx	at Time point T x : 
 
if HbA1c <math>\geq</math>7% OR daily insulin requirement <math>\geq</math>0.50 IU/Kg/day, then endpoint = 'No' (even in case of one missing component)
 
if HbA1c <7% AND daily insulin requirement <0.50 IU/Kg/day, then endpoint = 'Yes' (both component should be non-missing)
 

AUC	All AUC calculations (0-120min and 15-120min) will be based on actual rather than scheduled timings and will be calculated using the trapezoidal rule. In case of partial information collected during an assessment: 
 
if actual time is not recorded, the scheduled time will be used instead;
 
missing values will be imputed via linear interpolation;
 
when C-peptide values are below the limit of detection, the limit value (0.2 ng/mL, any exception will be clarified) will be assumed in the calculation of AUC.
 
 Basal value to be used in the AUC calculation is the Average Basal C-peptide (next section). The last non-missing time of Basal #1 and Basal #2 values will be used to calculate the time differences in the AUC. C-peptide 0-120 min AUC (nmol/L) values will be calculated based on all Basal-120min C-peptide values. C-peptide 15-120 min AUC above fasting (nmol/L) will be calculated based on the changes from Basal in 15-120min C-peptide values. Unscheduled assessments will be excluded from the analysis.
C-peptide parameters	Average Basal C-peptide (nmol/L) = Mean (Basal #1 C-peptide; Basal #2 C-peptide); C-peptide Cmax (nmol/L) = Maximum C-peptide value between post basal values; C-peptide Tmax (min) = Time at which the C-peptide Cmax is reached In case both Basal #1 and Basal #2 C-peptide are missing, the Average Basal C-peptide will be set as missing.
Time from T1D diagnosis to inform consent	Time from T1D diagnosis to IC (days) = Date of IC signature - Date of T1D diagnosis +1. Missing/partial dates will not be imputed. Anyway, since these dates are crucial for enrolment, their complete presence in the final database is expected.

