## 9.5. STATISTICAL METHODOLOGY

All patient data collected on the eCRF will be listed by patient and center.

Appropriate descriptive statistics will be produced, according to the variable. For continuous data n, mean, standard deviation, median and range (minimum and maximum) will be presented. For categorical data, frequency distributions and percentages will be presented. If appropriate, confidence intervals around the mean or the proportions will be presented.

All AUC analyses will be based on actual rather than scheduled timings and will be calculated using the trapezoidal rule. In case of partial information collected during an assessment:

- if actual time is not recorded, the scheduled time will be used instead;
- missing values will be imputed via linear interpolation;
- when C-peptide values are below the limit of detection, the limit value will be assumed in the calculation of area under the curve.

The last available basal sample (time and value) will be used as the first sample in the computation of the AUC. If required, inferential statistics will be conducted on  $\log(x+1)$  transformed data, according to Lachin [2011].

Unless otherwise specified, the significance level used for statistical testing will be 0.05 and one-sided tests will be used.

A Statistical Analysis Plan will be issued with more technical and detailed elaboration of the principal features of statistical analyses. Additional post-hoc analysis may be produced to further allow comparison between ladarixin and placebo, according to the results obtained.

Any deviations from the original statistical plan (including unplanned analyses) will be clearly documented in the Clinical Study Report.

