#### 14.3.5. Mixed Meal Tolerance Test

The MMTT will be performed after an overnight fast, according to [Greenbaum \(2008\)](#) at baseline (within 3 week prior of randomization) and at each subsequent visit at month 6, 12 and 18. MMTT should not be performed within one week of resolution of a diabetic ketoacidosis event, defined as the presence of:

- hyperglycemia (blood glucose >200 mg/dL);
- pH <7.3 or HCO3 <15;
- ketones positive in the serum or urine.

Prior to the test, patients will withhold long-acting insulin on the morning of the test. Rapid-acting and short-acting insulin will be allowed up to 6 hours and 2 hours, respectively, before the test. Test will be re-scheduled if the patient has a capillary glucose value of >200mg/dL or <70mg/dL.

The test will be initiated before 10 a.m. After 2 pre-meal basal samples have been drawn between -20 to 0 min (basal 1 and basal 2), patients will be given 6mL/kg of Boost® High Protein Nutritional Drink (Nestlé Nutrition) up to a maximum of 360mL, to be drunk within 5 min. Post-meal samples will be drawn at 15±5, 30±, 60±10, 90±10, 120±15, 120±15 min after the meal.

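### The 2-hour C-peptide AUC is an undivided area over actual sampling times, so its span can run from 105 to 155 minutes and its printed unit, nmol/L, does not fit

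*SAP*

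**What the plan says.** SAP 9.1, Table 3, sets the rule for both C-peptide areas: "All AUC calculations (0-120min and 15-120min) will be based on actual rather than scheduled timings and will be calculated using the trapezoidal rule". For the main one, "C-peptide 0-120 min AUC (nmol/L) values will be calculated based on all Basal-120min C-peptide values". The start point is also an actual time: "The last non-missing time of Basal #1 and Basal #2 values will be used to calculate the time differences in the AUC". The 15-120 minute area uses changes from basal and is likewise labelled nmol/L. SAP 7.3 prints nmol/L for both areas again.

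Protocol 14.3.5 gives the permitted sampling times. The two basal samples may be drawn between -20 and 0 minutes, and "Post-meal samples will be drawn at 15±5, 30±, 60±10, 90±10, 120±15, 120±15 min after the meal". The 30-minute tolerance is blank and the last entry is printed twice.

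Protocol 9.5 also specifies actual times and the trapezoidal rule, but takes the basal point differently: "The last available basal sample (time and value) will be used as the first sample in the computation of the AUC". Table 3 uses the mean of the two basal values, placed at the last basal time.

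SAP 7.2.1.3 compares the 2-hour AUC and its change from baseline between arms by t-test or Mann-Whitney test. SAP 7.2 plots both and prints significant p-values on the graphs.

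**The concern.** A trapezoidal area grows with the length of time it covers. If that length differs between patients or visits and is never divided out, part of each value reflects when the tube was filled and not how much C-peptide the patient made. A patient whose last sample is late gets a larger area from the same concentrations. Change from baseline carries this error from two visits.

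The unit points to the same gap. Concentration multiplied by minutes gives nmol/L x min; nmol/L is right only after division by time. Either the label is wrong or a division was meant and not written. Two programmers could follow Table 3 in good faith and produce results that differ by a factor of about 120.

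This is the trial's measure of beta-cell function, which Protocol 3.3 names as something the study was designed to evaluate. Enrolment stopped early, so avoidable noise costs relatively more.

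**Working it through.** The documents state no computed figure here; the only number to reproduce is the nominal 120 minutes.

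**Span of the area.** Span = (actual time of the last post-meal sample) - (actual time of the last non-missing basal sample). Inputs are the windows in Protocol 14.3.5.

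- Nominal: 120 - 0 = 120 min, as labelled.
- Shortest: 105 - 0 = 105 min (-12.5%).
- Longest: 135 - (-20) = 155 min (+29.2%).
- Last basal sample at 0: 105 to 135 min.
- 15-120 minute area: 105 - 20 = 85 min to 135 - 10 = 125 min, against a nominal 105.

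**Same C-peptide, different span.** For an assumed flat 0.6 nmol/L, area = 0.6 x span:

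- 105 min: 63.0 nmol/L x min
- 120 min: 72.0
- 155 min: 93.0

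The extremes differ by 155/105 - 1 = 48%. In a milder case, baseline sampled at 0 and 120 and Month 12 at 0 and 135, the change is 81.0 - 72.0 = +9.0 nmol/L x min with no change in C-peptide. Divided by span, every value is 0.6 nmol/L.

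**A rising profile.** Assumed values are 0.40, 0.55, 0.75, 0.95, 0.95, 0.85 nmol/L at 0, 15, 30, 60, 90, 120 min.

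- Nominal times: 7.125 + 9.75 + 25.5 + 28.5 + 27.0 = 97.875; divided by 120 = 0.816 nmol/L.
- Last sample at 105: the final term becomes 15 x 0.90 = 13.5, total 84.375 (-13.8%); divided by 105 = 0.804 (-1.5%).
- First at -20 and last at 135: the first term becomes 35 x 0.475 = 16.625 and the last 45 x 0.90 = 40.5, total 120.875 (+23.5%); divided by 155 = 0.780 (-4.4%).

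**Noise from timing alone.** This is a simulation on the same profile, with concentrations following the curve, flat before 0 and declining slightly after 120. The blank 30-minute tolerance is taken as ±5.

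- Times uniform over the full windows: CV of the area about 7.7%, falling to 1.6% to 1.9% after division. The lower figure takes the later of two basal draws, the higher a single draw.
- Basal fixed at 0: CV about 7.6%, so the ±15 minute final window drives the result, not the -20 minute case.
- Basal and final samples within 5 minutes of schedule: CV about 2.6%.

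**Basal value.** Protocol 9.5 uses the last basal sample's time and value. SAP Table 3 uses the last basal time with the average value. The two agree only when the two basal values are equal or one of them is missing.

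**The case against.** The strongest reply is that nmol/L shows a time-averaged AUC was intended all along. The only defect would then be an unstated divisor, and the relevant noise the smaller figure. That reading is plausible, but no passage in either document says so, and Table 3 as written yields the undivided area. Both readings lead to the same edit.

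Second, the extremes are corner cases. A start at -20 needs both basal draws at that time, or the later one missing, and sites will usually sample near schedule. This stands, and it is why the 2.6% figure belongs beside the 8%.

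Third, the practical cost is modest. If the between-patient CV were 30% to 60% (an assumption; the documents give none), independent timing noise of 7.7% would raise the cross-sectional SD by √(0.30² + 0.077²)/0.30 - 1, about 3%, down to about 1%. This also stands. The effect on change from baseline depends on within-patient correlation, which is not given.

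Fourth, this is one of ten secondary endpoints, and SAP 4.8 and 7 make every analysis descriptive. That limits the consequence. It does not make a mislabelled quantity readable.

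**Conclusion.** The point holds as a derivation rule that is wrong as written. The window is not fixed, the area is not divided by time, and the printed unit is not that of an area. The 105 to 155 minute span comes directly from the documents, for a complete test inside the protocol windows. If the 120-minute sample is missing, linear interpolation cannot supply an end point, and the area could stop at 80 minutes. The percentages and CVs rest on assumed profiles and timing distributions. The result is extra noise and an uncertain scale in a descriptive secondary endpoint. It is worth correcting, but does not threaten the trial's main conclusion.

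Four stronger readings are tempting and not supported:

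- A reader might infer a bias towards one arm. Sampling is blinded until the last patient's Month 12 visit, and nothing suggests that timing would differ by treatment.
- A reader might infer that the values cannot be compared between patients. They are noisier than necessary, which is a weaker statement.
- A reader might infer that the 0.2 ng/mL detection limit will be entered as nmol/L and inflate low values. Table 3 states the unit explicitly; a conversion is needed, but nothing says that it will be skipped.
- A reader might infer that SAP 4.8 should have listed the change in basal value. That section is confined to changes caused by the enrolment stop. The discrepancy with Protocol 9.5 is real, but its absence from 4.8 is not a separate error.

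**What to change.** In SAP Table 3, divide each trapezoidal area by the actual elapsed time between its first and last samples, and report the result in nmol/L. For 0-120 minutes this is mean C-peptide; for 15-120 minutes it is the mean rise above basal. The unit already printed in Table 3 and section 7.3 then becomes correct. Division does not remove timing effects completely, because pre-meal minutes still count (about 4% low in the -20 to 135 case above), but it removes most of them.

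Interpolating to exactly 120 minutes is not a substitute. A last sample at 105 to 119 minutes is allowed and would need extrapolation, and the result would still be in nmol/L x min.

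Separately, choose one basal value for the AUC, either the last sample as in Protocol 9.5 or the average as in Table 3. If the average is kept, record it as a change from the protocol, in the SAP or the clinical study report.

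The cost is one line in Table 3, one line of code and one sentence on the basal value. No new data are needed, because actual sampling times are already recorded.
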